In most of Malawi, including in Neno District, the usual care procedure for addressing depression is for patients who self-present with significant symptoms such as psychosis, suicidal ideation or attempt or potential harm to others receive a referral either to a mental health clinical officer or nurse within the district (in Neno District there are three), or else to a mental health specialist at a regional hospital. Due to the limited supply of mental health clinicians in Neno District, those with comorbid conditions such as schizophrenia or more complex mood disorders such as bipolar disorder are prioritized for immediate intervention. Of those who presently receive treatment for overt mood disorders, treatment typically comprises pharmacotherapy—including fluoxetine or amitriptyline for depressive symptoms with individual counseling if time and staff is available. There is currently no system-wide model in IC3 or primary services for screening for depression. However, Neno District has begun

screening and treatment for peripartum depression at one antenatal clinic—a system separate from the IC3 system which is the focus of this work. The inclusion of depression screening and psychoeducation, features of the control arm of this study, represent modest enhancements of the existing system from which the full IC3 model will be introduced.

With regard to IC3, services are condition-specific. To provide an example: HIV/AIDS is the most common chronic care condition treated at IC3, constituting approximately 70% of enrollees. Patients receiving antiretroviral therapy attend clinic every three to six months for evaluation (e.g. screening, adherence, viral load) and are provided with a necessary supply of antiretroviral medications until their scheduled return date. Patients with non-suppression, missed appointments or poor adherence are evaluated on a monthly basis. Non-communicable disease (NCD) patients attend clinic every 3 months with 1-month appointments with poor disease control or missed appointments. They are screened for comorbid disease (e.g. HIV, tuberculosis [TB], other NCDs) and provided with necessary supply of medications to their scheduled return date.

Treatment: IC3D

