All models will be estimated using restricted maximum likelihood using the R package lme4. We will report point estimates, confidence intervals, and p-values but not make any claims of “statistical significance” given recent strong arguments against doing so.⁸⁹ P-values will be based on the null hypotheses $H_0: \delta = 0$ versus the two-sided alternatives $H_1: \delta \neq 0$ in each of the models. Given there are multiple primary outcomes, we will adjust reported p-values for multiple testing using a stepdown method, which provides an efficient means of controlling the family-wise error rate.⁹⁰ We will derive the exact distributions of the test statistics to perform the stepdown procedure using a (pseudo-)permutation test approach, by re-randomizing clusters to different sequences in the stepped-wedge design 100,000 times.⁹¹ This method ensures appropriate control of the family-wise error rate and avoid potential biases resulting from small numbers of clusters.

Cost and cost-effectiveness analysis

The research team will employ time-driven activity-based costing (TDABC) to gather program costs before (Year 1) and after (Year 4) intervention roll-out. TDABC is a gold

standard, patient-centered approach: It begins by studying flow of patients through the health system, and then measuring human and other resources expended. Baseline costs, gathered in Y1, will assess cost of care as usual for individuals utilizing IC3s. A cycle of care will be annualized as four quarterly IC3 visits, inclusive of testing and labs, according to diagnosis. Itemized expenditures will be accrued from PIH's financial software system.⁹² To assess economic costs, such as subsidized ARVs by PEPFAR, we will use external cost sources such as management Science for Health's International Medical Product Price Guide (MSH-IMPPG).⁹³ As the cost comparator, we will replicate the cost exercise in Year 4, when depression care is operating at scale, again tracing individuals according to service type—now including depression care.

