Health measures will be converted to quality-adjusted life years (QALYs) using the EQ-5D-3L cross-walk between domain-specific outcomes.¹¹ QALY estimates will be related to base case and treatment cost estimates. For formal CEA, we will use a gold standard Markov chain Monte Carlo (MCMC) simulation-based approach⁹⁴ in TreeAge,⁹⁵ from a societal perspective.⁹⁶ For sensitivity analyses, we will vary discount rates from 0-5%, based on health-adjusted life expectancy.⁹⁷ Unit of interest is the incremental cost-effectiveness ratio (ICER) of cost per QALY, comparing the cost of integrated chronic care before and after introduction of the depression treatment.

Ethics

The study protocol has been reviewed and approved by the National Health and Science Research Council administered by the Government of Malawi, and by the RAND Corporation in Santa Monica, California. Any protocol modifications will be submitted to the IRB for review,

and participants will be informed if warranted. The trial is registered with the NIH clinical trial registry (clinicaltrials.gov) and assigned the number NCT04777006.

We do not expect any medication-related adverse events beyond that of routine medical care and use of antidepressant therapy. All potential side effects will be outlined to patients during the informed consent process. Patients will be assessed and monitored with regards to psychiatric symptoms and treatment side effects by their provider on a standardized schedule using the Antidepressant Side Effect Checklist.

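### The planned ICER has no single comparator: costs are set against Year 1 care without depression screening, while the only planned patient utility contrast is against a control state that already has screening, diagnostic interview and psychoeducation

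*Protocol*

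**What the plan says.** **Cost side** (Protocol, Cost and cost-effectiveness analysis). The team will "gather program costs before (Year 1) and after (Year 4) intervention roll-out". For the first costing, "Baseline costs, gathered in Y1, will assess cost of care as usual". For the second, "we will replicate the cost exercise in Year 4, when depression care is operating at scale". The ICER is then described as "comparing the cost of integrated chronic care before and after introduction of the depression treatment". No price year is stated; the only sensitivity analysis named varies the discount rate.

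**What Year 1 care contains** (Protocol, Treatment: Usual Care). "There is currently no system-wide model in IC3 or primary services for screening for depression". Table 1, as extracted, marks cost-effectiveness work in Year 1 Q3–Q4 and starts eligibility screening in Year 2 Q1, so the Year 1 costing comes before trial screening.

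**What the control state contains.** The same Usual Care section says: "The inclusion of depression screening and psychoeducation, features of the control arm of this study, represent modest enhancements of the existing system". The SAP addendum on implementation outcomes adds that screening and diagnosis measures exist in both conditions.

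**Effect side.** In the Protocol's analysis section and in the SAP, the ITT treatment indicator contrasts a clinic in the intervention state with a clinic in that control state. Patient EQ-5D is collected only from people enrolled or diagnosed with depression (Protocol, Overall health; SAP, Analysis of Primary Outcomes). On the QALY input, the cost-effectiveness section says only that QALYs will be linked to base-case and treatment costs within a simulation model.

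**The concern.** Usual care carries two meanings. In the costing section it is unscreened Year 1 care. In the trial it is the enhanced control. The IC3D section describes the intervention as usual care with PM+ and antidepressant therapy added, so screening is not part of the randomised increment. Yet a Year 4 minus Year 1 cost difference includes it.

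If the trial effect supplies the QALY gain, the numerator pays for screening all attendees, interviewing and psychoeducation, while the denominator omits any health gain from those activities because control clinics have them too. The ratio then matches IC3D against the trial control only if those activities cost nothing, and IC3D against unscreened care only if they bring no QALY benefit.

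Cost-effectiveness is a stated aim, and the Discussion rests its case for scale-up on it. A before/after cost difference over about three years also picks up price change unless both costings are valued at one price year.

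**Working it through.** The documents give no cost, QALY gain or ICER, so there is no figure to reproduce. The check is algebraic.

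**Notation.** 0 = Year 1 care without screening; c = trial control (usual care plus screening, interview and psychoeducation); 1 = IC3D. C is cost and E is QALYs.

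**Three ratios**
- Mixed, if the stated costing is combined with the trial effect: (C1 − C0)/(E1 − Ec)
- Matched to the trial control: (C1 − Cc)/(E1 − Ec)
- Matched to unscreened usual care: (C1 − C0)/(E1 − E0)

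**Distortion**
- Let s = (Cc − C0)/(C1 − C0). Then C1 − Cc = (1 − s)(C1 − C0), and mixed ÷ matched-to-control = 1/(1 − s).
- Let e = (Ec − E0)/(E1 − E0). Then E1 − Ec = (1 − e)(E1 − E0), and mixed ÷ matched-to-usual-care = 1/(1 − e).

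Both factors are at least 1 when the control-state activities have non-negative cost and benefit (s and e between 0 and 1). The values of s and e below are assumptions:

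| s or e | Factor |
|---|---|
| 0% | 1.00 |
| 5% | 1.05 |
| 10% | 1.11 |
| 20% | 1.25 |
| 30% | 1.43 |
| 50% | 2.00 |

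**Could s be trivial?** All attendees are screened. At the 10% prevalence in the Sample Size section, about 1/0.10 = 10 people are screened per case. The 13,000 IC3 patients in 2020 and 14 × 30 = 420 enrollees per step give 13,000/420 ≈ 31 per enrollee. That is an upper bound, because the 13,000 is not limited to adults and some HIV patients attend only six-monthly. Screening cost per treated patient therefore need not be negligible, but its size is unknown.

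**Price level.** If prices were left nominal over three years at an assumed annual growth r, the drift is (1 + r)³ − 1: 9.3% at 3%, 15.8% at 5%, 33.1% at 10%. It applies to the whole Year 1 cost of IC3 care, not just the increment. For a true increment that is a share k of baseline cost, the undeflated difference divided by the true one (in Year 4 prices) is 1 + [1 − 1/(1 + r)³]/k. At r = 5% and an assumed k = 20%: 1 + (1 − 1/1.1576)/0.20 = 1.68. This is an illustration; the plan does not say that nominal prices will be used.

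**The case against.** The strongest reply is that the effect comparator is inferred. The cost-effectiveness section never says that the trial's treatment coefficient is the QALY input, and the simulation model could adjust for the control state. Indirect benefits, such as comorbid conditions and household burden, are also to be included. This stands, and it limits the point to a strong inference. The inference is strong because no patient utility data are planned from an unscreened state and no adjustment is described.

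A reader might infer that screening should not be charged to IC3D at all. The documents do not support that. The stated aim under Study Design is the incremental cost of IC3D over usual care within IC3, screening is named in the project title, and a ministry scaling up the model would have to pay for it. For that question only the 1/(1 − e) factor remains. The Protocol calls the control-state additions modest, so e may be small, but the planned data cannot estimate it.

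A reader might also infer that case-mix drift passes straight into the cost difference. It is partly handled: a cycle of care is costed by diagnosis, and patients are traced by service type.

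Finally, the comparator mismatch can only raise cost per QALY under the conditions above, so it works against the protocol's expectation of high cost-effectiveness. That is correct for the comparator issue. Change between the two costings for other reasons could go either way.

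**Conclusion.** The point holds in this form: followed as written, the costing rule and the only planned patient utility contrast use different reference states, and the plan does not reconcile them. This is more than missing detail, because the cost comparator is stated explicitly.

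The documents do not support the stronger conclusion that the ICER is wrong. No ICER exists yet, the effect input is not named, and with e = 0 the mixed ratio equals the one for IC3D against unscreened care. The conditional size is a factor of 1.11 at 10% and 1.25 at 20%, for s against the trial control and for e against usual care. Both shares, and any price growth, are assumptions.

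The conclusion rests on the trial effect being the QALY input, on non-negative cost and benefit of the control-state activities, and on the column positions of Table 1 as extracted. The content of Figure 3 was not available.

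**What to change.** Amend the Protocol's costing section as follows.

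1. In the Year 4 activity-based costing, itemise screening, diagnostic interview and psychoeducation separately from PM+ and antidepressant therapy.
2. Report two labelled ICERs: IC3D against the trial control, with the itemised activities costed in both states; and IC3D against Year 1 care without screening.
3. For the second, state the assumption that control-state activities give no QALY benefit (e = 0), and vary e in sensitivity analysis.
4. Name the effect input to the simulation model for each ratio.
5. Value Year 1 and Year 4 resource use at one stated price year.

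For step 2, activity volumes in the control state can draw on the SAP addendum's screening and diagnosis proportions, which are available in both conditions.

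The cost is a little more analysis work. The costing method already follows patient flow and measures resources used, so itemising fits within it. Costing clinics in their Pre periods is not required: in Figure 1 the last Pre month is month 15, so none would remain in Year 4 and it would mean an extra costing round. Which of the two ratios leads is the sponsor's choice.

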Integrating a Stepped Care Model of Screening and Treatment for
Depression into Malawi's National HIV Care Delivery Platform

(ID: R01MH117760)

Statistical Analysis Plan

Analysis of Primary Outcomes

This analysis plan concerns the primary outcomes of the IC3D intervention trial. However, analyses of the secondary outcomes will follow the same procedure with appropriate changes for the nature of the outcome.

We will have primary outcomes at two levels. At the aggregate cluster-time level we have

1. Prevalence of depression

As we do not capture data on those who do not have depression that would enable us to link individual screening outcomes between time periods, we will only be able to collect total number screened and total number with depression for each cluster at each time period (i.e. "step").

At the individual level, among those who are diagnosed with depression we will collect:

2. Depression severity among those with depression (PHQ-9)
3. WHODAS score among those with depression
4. EQ-5D-3L utility score and those with depression

If the intervention is successful then it should have the effect of reducing the overall prevalence of depression among those with chronic conditions, and also reduce the severity of depression and improve the quality of life among those with depression in this group of patients.

The data derived from the trial will be analysed using a generalised linear mixed model framework standard for stepped-wedge cluster designs.[1] Several trial guidelines, including the influential CONSORT statement,[2,3] recommend the specification of a single primary outcome to avoid a multiple comparisons problem. However, given the complex, multifaceted nature of this health service delivery intervention, no single outcome can adequately describe the effect of the intervention and be used to judge its effects. As a result, we have specified several primary outcomes and will "correct" or modify our analyses to account for the multiple outcomes problem.

There are two main types of approach to dealing with multiple outcomes: multivariate methods and univariate methods. The former method works by jointly modelling all the outcomes at once. However, the joint model of the four outcomes is highly complex, potentially with non-linear sub-models, two-stage models, and shared random effects to allow for correlation (see Appendix), which makes inference difficult or even infeasible without development (and evaluation) of custom software (e.g. a Monte Carlo Maximum Likelihood sampler), which is out of the scope of this project. Instead, we will model the outcomes separately and use a method to correct the family-wise error rate (a univariate methodology).

Statistical model

Aggregate cluster-time outcome

For cluster $j = 1, \dots, J$ at time period $t = 1, \dots, T$ we will screen n_{jt} patients of whom $y_{jt}^{(1)}$ will be diagnosed with depression such that

$$y_{jt}^{(1)} \sim \text{Binomial}(n_{jt}, p_{jt})$$

where we will specify a logistic regression model:

$$\log\left(\frac{p_{jt}}{1-p_{jt}}\right) = z'_{jt}\gamma_1 + \delta_1 D_{jt} + \alpha_{j,1} + \phi_{jt,1}$$

where z_{jt} is a vector of cluster-level covariates, and $\alpha_j \sim N(0, \sigma_\alpha^2)$ and $\phi_{jt} \sim N(0, \sigma_\phi^2)$ are cluster and cluster-time random effects, respectively.

Individual-level outcomes

For patient $i = 1, \dots, N$ who has depression the outcome is $y_{ijt}^{(k)}$ for outcomes $k = 2, 3, 4$. For each outcome we specify the linear model:

$$y_{ijt}^{(k)} = x'_{ijt}\beta_k + z'_{jt}\gamma_k + \delta_k D_{(i)jt} + \theta_{i,k} + \alpha_{j,k} + \phi_{jt,k} + e_{ijt,k}$$

where x_{ijt} is a vector of patient-level covariates $\theta_i \sim N(0, \sigma_\theta^2)$ is an individual-level random effect and e_{ijt} is an independent, identically distributed error term.

The parameters of interest are δ_k , which are a (log) odds-ratio for the prevalence outcome and a mean absolute difference in score for the three individual-level outcomes. We will take both intention to treat (ITT) and per protocol approaches for the individual level outcomes. For the ITT analysis, the variable D_{jt} is an indicator equal to one if cluster j is in the intervention state at time t and zero otherwise. Thus, δ represents our estimated treatment effect. For the per protocol analysis, D_{ijt} will be a patient-level variable equal to one if the clinic was in the intervention state and the patient completed the treatment as defined above, and zero otherwise. As we describe below, we will use a randomisation test method to derive exact inferential statistics (p-values and confidence intervals) for the parameters of interest.

Outcomes 2-4 described above are only recorded for those who screen positive for depression at their scheduled visit. Thus, the data do not all cover the full patient population: data for outcomes 2 to 4 are a subset of those for outcome 1. Based on this, we anticipate the data to be normally distributed. However, we will test this assumption by examining QQ plots and conducting KS (Kolmogorov Smirnov) and SW (Shapiro Wilk) tests. In the event the normality assumption is violated, we will consider an alternative specification, such as a two-part semi-continuous model.

Statistical Inference

All models will be estimated separately using restricted maximum likelihood, using the R package lme4. We will report point estimates, confidence intervals, and p-values but not make any claims of "statistical significance", given recent strong arguments against doing so [2].

P-values will be based on the null hypotheses $H_0: \delta_k = 0$ versus the two-sided alternatives $H_1: \delta_k \neq 0$ in each of the models defined above. Given that there are multiple primary outcomes, we will adjust reported p-values for multiple testing using a cluster-based stepdown method, which provides an efficient means of controlling the family-wise error rate [18]. The full methodology is described elsewhere, but we describe it here briefly.

Let there be P hypotheses to be tested H_1, \dots, H_P with associated test statistics T_p . We let the ordered test statistics be:

$$T_{[1]} \geq T_{[2]} \geq \dots \geq T_{[P]}$$

corresponding to hypotheses $H_{[1]}, \dots, H_{[P]}$. The family of hypotheses being tested is $K \subset \{1, \dots, P\}$. We first describe a stepdown procedure for the decision to accept/reject given a value for the type I error rate α , as this provides a clear way of deriving the associated p-value that we will report.[4] The stepdown method works by firstly testing if the joint null hypothesis is true by comparing the largest test statistic to the critical value $c_K \left(1 - \frac{\alpha}{2}\right)$. If it is smaller than this critical value, we accept all null hypotheses; otherwise, we reject $H_{[1]}$ and test the remaining hypotheses as a new family in the same way. More specifically, the algorithm is:

1. Let $K_1 = \{1, \dots, P\}$. If $T_{[1]} \leq c_{K_1} \left(1 - \frac{\alpha}{2}\right)$, then accept all hypotheses and stop, otherwise reject $H_{[1]}$ and continue.
2. Let K_2 be the indices of hypotheses not previously rejected. If $T_{[2]} \leq c_{K_2} \left(1 - \frac{\alpha}{2}\right)$ then accept all remaining hypotheses, otherwise reject $H_{[2]}$ and continue.

The critical values here are the $1 - \frac{\alpha}{2}$ quantiles of the distribution of the largest test statistic for the relevant family of hypotheses. Exact distributions may not exist; however, we can derive them using a pseudo-permutation testing approach by enumerating a large number of permutations (e.g. 100,000 permutations) following a randomisation test approach based on the cluster randomisation.

At each stage of the stepdown algorithm, we are testing the largest test statistic, that is: $T_K = \max_{q \in K} T_q$. If the associated hypothesis is rejected, we create a new family of hypotheses that excludes the rejected hypothesis. If we re-randomise the clusters, then for each permutation $m = 1, \dots, M$, we can re-calculate the desired test statistic, $T_K^{(m)}$, to create our reference distribution. The p-value is then:

$$p_{[k]} = \frac{1}{M} \sum_{m=1}^M I(T_K^{(m)} \geq T_K)$$

That is to say that the reference distribution for the largest test statistic is the largest test statistic from the permutations of the remaining hypotheses, and so on (see also [4–6]). The test statistics we will use are the studentised, generalised residuals from each of the models, which are optimal for randomisation tests for cluster-based analyses and exponential family models,[7] and also ensure each of the individual tests in the family of tests has the same power since the test statistics will be of equivalent scale.[5]

The procedure above can be used to derive a set of confidence intervals for the parameters of interest that has nominal “family-wise coverage”, as described by Watson et al [TBA]. We will estimate 95% confidence intervals for the set of treatment effect parameters following this method.

Missing Data

We foresee the main risk in terms of missing data to be patients whose depression status may cause them to miss appointments and hence have fewer observations during the trial. This mechanism would generate data missing *not at random* (MNAR). Alternative mechanisms include data entry error and (conditionally) random patient no-shows to appointments (e.g. older patients are less likely to attend), both of which would be missing at random (MAR) or missing completely at random (MCAR). It is not possible to distinguish between MNAR and

MAR empirically.[8] Thus, to provide information about the possible mechanism of missingness in the data, CHWs tasked with following-up with patients will be asked to identify a main reason for the missed appointments in an anonymous reporting form. For example, reasons may include “mental health/emotional issues” or alternative such as “was not able to attend due to other commitments”. A qualitative judgement will be made on the basis of these data by the trial team as to what the most likely/common cause of missingness is likely to be. We also note that the CHW follow-up process should also limit the extent of missing data in this study.

If the data are considered to be (mostly) MAR or MCAR then they do not present a risk of bias for our analyses; however, the uncertainty may be under-estimated. If this is the case, and there exists a substantial proportion (> 10% missing) of missing data, then a secondary analysis will be conducted using multiple imputation methods. If the data are determined to be (mostly) MNAR then a secondary analysis that attempts to jointly model the outcome, covariates, and missingness mechanism will be conducted: in particular, a random coefficient pattern mixture model approach will be used, which has previously been shown to provide reliable inferences for longitudinal data with MNAR data, particularly in the case where drop out may be due to a decline in functioning over time.[9]

Secondary Outcomes

The analysis plan will also include several secondary analyses, in which we focus on the relationships between the intervention and physical health outcomes—such as HIV, diabetes, and hypertension—as well as theoretical moderators, including fidelity to protocols among providers, levels of social support received by participants, and perceived internalized stigma among patients. For physical health outcomes, the same model specification will be used as described above. For evaluation of the effect of the intervention on potential moderators, the relationships will predominately be examined through interaction models, in which we will include an interaction term of the treatment effect with variables measuring fidelity, social support and stigma in the models. While examining the relationships among these variables, the research team may also consider mediator pathways for social support and stigma, whereby the intervention leads to changes in social support and stigma, which (in turn) lead to reductions in depression symptoms.

Addendum: Added 18 November, 2021

Implementation outcomes

We propose to add a more detailed and explicit assessment of the implementation of the intervention as a secondary analysis. The primary aim of the trial remains to estimate the effectiveness of the intervention from an intention-to-treat perspective. However, given the novelty of our approach, understanding the context for implementation and the barriers to successful adoption and integration of mental health interventions is an important secondary aim. The trial is thus a “hybrid effectiveness-implementation trial” according to the schema outlined by Wolfenden et al. (2021) [10]

The implementation outcomes are divided into three categories:

1. Screening:
 - a. Proportion of patients screened with the PHQ-2, out of those attending IC3 clinics.
 - b. Proportion screening positive with PHQ-2, out of those who were administered the PHQ-2.
 - c. Proportion screened on the PHQ-9, out of those who screened positive on the PHQ-2.
 - d. Proportion screening positive on PHQ-9, out of those who were administered the PHQ-2.
2. Diagnosis:
 - a. Proportion of patients who are administered the BDIS, out of those who screened positive on the PHQ-9.
 - b. Proportion of patients who receive a diagnosis using BDIS, out of those administered the BDIS.
3. Treatment:
 - a. Proportion of patients attending treatment sessions (PM+, ADT, both), out of those who have been enrolled in the IC3D clinical trial and elected to receive treatment (PM+, ADT, both)
4. Protocol Fidelity:
 - a. Proportion of reviewed mastercards appropriately completed by clinical officers
 - b. Proportion of patient registration forms appropriately completed by counsellors
 - c. Proportion of PM+ components appropriately covered within each PM+ therapy session

Each step is a potential point of failure that could limit the acceptability or effectiveness of the intervention. Analysis of the implementation outcomes constitutes a descriptive analysis intended to support interpretation of trial results.

We will report the overall trial mean proportions of each implementation outcome along with 95% confidence intervals. Note that the screening and diagnosis outcomes are available for both treatment and control conditions, while the treatment outcomes are only available in treatment units. We will also examine the temporal changes in the implementation outcomes by reporting within each three-month block mean proportions and associated uncertainty intervals.

Secondary analyses

In addition to the usual issues of adherence, such as patients refusing treatment or not attending scheduled treatment, we have identified that patients diagnosed in one month or trial “block” may not be treated until the subsequent month or trial block. At an individual level, non-adherence would

